12.4 Protections against Risk

Investigators will make all efforts to minimize the physical, psychological, privacy and confidentiality risks to human subjects.

Physical Risks: In regard to screening for study entry, patients' discovered to have a clinical/laboratory contraindication for PrEP will be informed and educated by the PI regarding the reason for their ineligibility. Clinical/laboratory abnormalities will be addressed using standard ED protocols. Patients with a primary care provider will be referred back to their doctor for further management. For patients without a primary care provider follow-up will depend on the specific exclusion criteria. Patients with decreased eCrCL will be referred to out-patient nephrology. Patients found to have HBsAg+ will be referred to out-patient Hepatology. Patients found to be HIV+ will be immediately linked to care at Peter Krueger Clinic as per standard ED protocols. Patients found to be pregnant will be referred to out-patient Obstetrics and Gynecology.

All patients initiated on PrEP in the ED will be monitored by the study team for the first 14-days (the duration of the starter pack) or until linked to their outpatient PrEP provider. While we will not be dictating out-patient clinical care we expect that patients will be managed as recommended in the US Public Health Service Pre-Exposure Prophylaxis Clinical Practice Guidelines. This includes repeat HIV testing every 3-months, repeat pregnancy testing for women who may become pregnant, STI testing for sexually active persons with signs or symptoms of infection and eCrCL monitoring (every 6-months).

Psychological Risks: Patients may suffer from anxiety and discomfort at any point during the study. This could be the result of learning that they have one of the medical exclusion criteria or PrEP initiation or a sexually transmitted infection. The RAs will undergo extensive training with the New York City Department of Health and Mental Hygiene (NYC DOHMH) to learn the appropriate counseling skills to address patients concerns. In the event that a RA needs additional assistance they will reach out to the Principle Investigator or social workers from the Emergency Department.

Privacy and Confidentiality Risks: The PI, the project manager (PM), and RAs will have access to identifiable study data. All hardcopy will be kept in a locked file cabinet in the PI's locked office. All study data will be entered into a password protected REDCap database or local databases behind the Mount Sinai firewall. The participant's anonymous study ID will be used on a linking sheet to connect survey data with medical chart review data. Otherwise, identifiable data will not be shared outside of Mount Sinai. All data shared outside of Mount Sinai (with biostatisticians) will be stripped of identifiers and transmitted via encrypted email message.

All possible steps will be taken to protect the participants against the unlikely and minimal risks described above. In order to ensure patient confidentiality, the following measures are proposed. Electronic data will be stored in password-encrypted files and transmitted by the research coordinator via secure, encrypted email to the PI. All paper data forms (used only when internet access is not available in the ED to permit data entry directly into REDCap), will be housed in a locked file cabinet within the PI's office until they are batched and brought in person to the RA for data entry. The RA will check the forms for completeness and enter all data into the REDCap database. The study database will be password-protected and encrypted and data files will be backed up routinely to guard against losses. Access to the study database will be limited to the study personnel.

All additional protections of participant confidentiality mandated by the Health Insurance Portability and Accountability Act (HIPAA) will be strictly followed. Additionally, the following data safeguarding procedures will be observed: 1) training staff on data sensitivity and data safeguards being employed to assure confidentiality, 2) storing and processing a hard copy in a centralized location, 3) securing a sensitive hard copy in a locked file, 4) destroying all identifiable linkages to data after data accuracy has been verified and final analyses have been computed, and 5) protecting the database by encrypted password. An encrypted master list of name to participant ID number will be kept by the PI separately in a locked location.

If at any time, a subject expresses verbal or nonverbal unwillingness to participate in any of the components of this proposal, the subject will be withdrawn from the study.

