2.0 STUDY SYNOPSIS

This study will recruit and randomize 80 HIV Pre-Exposure Prophylaxis (PrEP) eligible Emergency Department (ED) patients to facilitated linkage to care for PrEP initiation versus immediate PrEP initiation in the ED (iPrEP) using a PrEP starter pack with facilitated linkage to care. The primary outcome is PrEP usage at 90 days post enrollment. Multiple secondary outcomes will also be measured including retention in care, STI diagnosis, risk behavior and PrEP adherence at 30, 60, and 90 days.

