Patients will be instructed at the time of discharge that they will be contacted by a member of the PrEP Warm Line to schedule follow-up with a PrEP provider. The decision to start PrEP for those not randomized to the iPrEP arm or to stop or continue PrEP for those randomized to the iPrEP arm will be a decision made by the patient in conjunction with their PrEP provider. The ED clinical team will be available to assist patients should have they have any concerns or problems before that linkage occurs. For those randomized to the iPrEP arm if they have any side-effects within the first 14-days of starter pack use they will contact the study team and a decision to continue or stop PrEP will be made after a discussion between the patient and the PI. All patients enrolled in the study will receive standard PrEP counseling which includes information about the need for frequent HIV testing and risk reduction strategies. The importance of follow-up with the PrEP provider will be stressed. We do not anticipate the need for any re-testing (HIV, LFTs, eCrCL) by the study team after ED discharge. These tests are not typically recommended until the patient has been on PrEP for at least 30 days and sometimes not until 90-days. All recommended follow-up testing will be the responsibility of the clinical PrEP provider.

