11.1.2 Analysis of Primary and Secondary Outcomes

Analysis will be on an intention-to-treat basis. In statistical analyses, participants will be included to the date of their last active follow-up visit. Comparisons between control and experimental (iPrEP) arms. To assess the success of randomization, a summary of the baseline variables by treatment group will be tabulated and univariate comparisons performed. The primary outcome, retention in care and PrEP usage, will be compared with proportions and Fisher's exact derived confidence intervals. Secondary outcomes: Secondary analysis will focus on determining how retention in care, risk behavior, adherence or STI diagnosis differ between the groups at any of the follow-up time points. PrEP adherence based on pill counts will be calculated by dividing the number of pills taken by the number of pills prescribed. Adherence will be calculated by study month for each participant. Group adherence comparisons will be compared using Wilcoxon rank sum test. Retention in care, STI diagnosis and risk behavior at each time point will be analyzed for each study visit. Retention in care and STI diagnosis will be treated as dichotomous variables for analysis. Measures of risk behavior will include consistency of condom use and number of sexual partners since prior study visit. Condom use will be treated as an ordinal variable and number of sexual partners as a continuous variable for analysis.

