12.1.2 Human Subjects Involvement, Characteristics, and Design

Aim 1 includes examining the impact of iPrEP initiation in the ED by providing a 14-day PrEP “starter pack” and creating linkage with the primary outcome being PrEP usage at 90-days post index visit compared to the linkage only arm, as well as a number of exploratory secondary outcomes including PrEP initiation

and use at 30 and 60 days. We also will collect data on recruitment and attrition rates, as well as means and standard deviations for key measures that will be needed to plan a definitive trial of ED-initiated PrEP.

For Aim 1, we will perform a randomized controlled clinical trial to compare the impact of immediate PrEP initiation (iPrEP) in the ED by providing a PrEP “starter pack” with facilitated linkage alone. The primary outcome is PrEP usage at 90-days post PrEP initiation visit. Participants will provide written informed consent for study participation. The consent to participate will also include 1) consent for investigators to collect prospectively collect clinical and sociodemographic data via medical record review and electronic data capture from the electronic health record. We anticipate 80 patients participating in the study associated with Aim 1.

Study procedures:

Aim 1: 80 PrEP eligible patients will be randomized 1:1 to either the experimental (iPrEP) arm or standard (outpatient PrEP) initiation arm. Patients in the iPrEP arm will receive a 14-day starter pack of PrEP and facilitated linkage. Patient in the control arm will receive facilitated linkage only. Patients in both arms will be followed for 90-days with telephone call follow-up visits scheduled for 30, 60 and 90 days post enrollment. Patients will be asked to complete satisfaction and medication adherence questionnaires at each scheduled follow-up

The setting of the human subjects' will be Mount Sinai Beth Israel Emergency Department.

Subject populations: The study population will include patients recruited in the Emergency Department at Mount Sinai Beth Israel Hospital

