To maximize retention we will use a Locator Form to collect the study participants current address, email address, phone numbers and, with consent, private social media information. In order to facilitate linkage and follow-up, we will also collect similar information for friends and family who know how to reach the patient. All follow-up assessments will be conducted at 30, 60, and 90 from PrEP initiation. All follow-up assessments will be conducted by telephone. Patients will be mailed an appointment reminder and receive a phone call a week and a day before their scheduled assessment. Patients who miss one or more than one follow-up assessment will continue in the study so long as it is within 90 days of their enrollment.

We will provide a \$25 cash incentive for all participants to complete their enrollment, 30, 60 and 90-day follow-up assessments.

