18.9 Participant Withdrawal

The PI will apply his/her judgement to determine whether or not an adverse event is of sufficient severity to require that the participant be withdrawn from further study medication. A participant may also voluntarily withdraw from treatment due to what he/she perceives as an intolerable adverse event or for any other reason. If voluntary withdrawal is requested within the first 14-day and the patient was assigned to the iPrEP arm, the participant will be asked to complete an end-of-study medication visit to return unused medication and document end-of-medication outcomes.

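### Section 12.4, read literally, ends study participation for anyone unwilling to take part in one component, so day-90 PrEP use could go uncollected, possibly unevenly between arms; it must be reconciled with Sections 9.3, 17.2 and 18.9

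*Combined protocol and SAP*

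**What the plan says.** The closing sentence of Section 12.4, under privacy and confidentiality, applies at any time and to verbal or nonverbal signals. It says that on "unwillingness to participate in any of the components of this proposal, the subject will be withdrawn from the study". Components are not defined.

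Other sections handle stopping PrEP differently:

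- Section 18.9: "A participant may also voluntarily withdraw from treatment due to what he/she perceives as an intolerable adverse event or for any other reason". It adds an end-of-medication visit for iPrEP participants who withdraw in the first 14 days, and does not say whether later calls go ahead.
- Section 9.3: the choice is described as "to stop or continue PrEP for those randomized to the iPrEP arm will be a decision made by the patient in conjunction with their PrEP", meaning the outpatient clinician. Side effects during the starter pack lead to a decision with the PI. Neither is said to end study participation. The same section does end participation when a clinical contraindication is found.
- Section 17.2: people who wish to discontinue are advised to have an HIV test and are asked why. Separately, iPrEP participants with a listed safety concern during the 14 days are withdrawn from the study.
- Section 10.5.7: the side-effect form is limited to people taking PrEP, which implies that follow-up also reaches people who are not.

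On the experimental arm, Section 12.1.2 says "Patients in the iPrEP arm will receive a 14-day starter pack of PrEP and facilitated linkage". For the comparison group the same section states: "Patient in the control arm will receive facilitated linkage only". On the outcome, Section 2.0 says "The primary outcome is PrEP usage at 90 days post enrollment". On the analysis, Section 11.1.2 says "Analysis will be on an intention-to-treat basis" but includes participants only up to their last active visit, and Section 11.1.1 excludes imputation.

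**The concern.** Refusing a treatment and leaving a study are different events, and an intention-to-treat comparison depends on keeping them apart. The literal wording of Section 12.4 merges them. An iPrEP participant who refuses the ED dose or hands back the pack is unwilling toward one component and, on that wording, leaves the study.

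Two things are at stake. The first is the primary outcome. Willingness to take PrEP is closely tied to PrEP use at day 90, so losing people because they did not want it is outcome-related loss. Part of that trigger exists in one arm only. The second is Aim 1b, which is meant to supply attrition rates for the definitive trial. Under the literal rule, PrEP refusal would be counted there as dropout.

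**Working it through.** **Step 1. Does withdrawal remove the day-90 value?** No section says that outcomes are collected after withdrawal from the study. With data used only to the last active visit and no imputation, a withdrawn participant has no planned day-90 value. Counting such people as non-users would keep them in the denominator, but the plan does not specify that. Provider or record verification of PrEP care (Sections 9.5 and 10.5.1, Engagement in Treatment Survey) could still supply the value, but the plan does not say that it continues after withdrawal.

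**Step 2. Who meets the trigger?**

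| Component | iPrEP | Control |
|---|---|---|
| Facilitated linkage | yes | yes |
| Calls and questionnaires | yes | yes |
| Laboratory tests | yes | yes |
| First dose in the ED | yes | no |
| 14-day starter pack | yes | no |

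The rule covers both arms, but two of the triggers exist only in iPrEP. The literal reading is stronger for declining the pack, on which no other section speaks directly, than for stopping it, which Sections 9.3, 17.2 and 18.9 address.

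**Step 3. Illustration.** Inputs from Section 11.1.3 are 40 per arm and a 50% control rate. Exact enumeration of the two-sided pooled Z test with 40 per arm reproduces all seven powers printed there (0.0812 to 0.9327). The documents give no refusal rate, so the number withdrawn, w = 2 to 8 of 40, is assumed.

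Assume 20/40 true users in each arm (no effect), no control withdrawals, and every withdrawn iPrEP participant a non-user. Observed iPrEP usage is then 20/(40 − w):

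| w | Observed iPrEP | Difference from 50% |
|---|---|---|
| 0 | 20/40 = 50.0% | 0 |
| 2 | 20/38 = 52.6% | +2.6 points |
| 4 | 20/36 = 55.6% | +5.6 points |
| 8 | 20/32 = 62.5% | +12.5 points |

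Treating the observed rate as the binomial rate, the chance of a two-sided Fisher p ≤ 0.05 is 3.3%, 4.8%, 6.3% and 14.1% for w = 0, 2, 4 and 8.

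**Step 4. Vary the assumptions.**

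- If 4 non-users leave each arm: 20/36 − 20/36 = 0.
- If half of 8 withdrawn iPrEP participants are users: (20 − 4)/32 = 16/32 = 50%, so no bias.
- If a quarter of 8 are users: (20 − 2)/32 = 18/32 = 56.3%, or +6.3 points.
- If 4 non-users leave control only, for example by refusing linkage: 20/40 − 20/36 = −5.6 points, so the sign reverses.

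**Step 5. Attrition.** Withdrawing 2, 4 or 8 of 40 for refusal adds 2/40 = 5%, 4/40 = 10% or 8/40 = 20% to the iPrEP attrition rate. Section 17.2 expects follow-up near 85%, a loss of about 15%, or 6 of 40.

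**The case against.** The sentence in Section 12.4 is a general statement of voluntariness at the end of a privacy paragraph. It does not mention PrEP, and the text that deals specifically with stopping PrEP does not remove the person from the study. A reader might infer that every participant who declines or stops the starter pack loses day-90 follow-up. The documents do not support that as a settled consequence: it is the literal reading of one sentence, in conflict with others. This part of the objection stands.

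A reader might also infer that likely failures are lost from the experimental arm alone. That does not follow either. Linkage is a component of both arms and the control arm's route to PrEP. A control participant who refuses it meets the same trigger and is also a likely non-user. Only the ED-dose and starter-pack triggers are one-sided, and the net direction of bias is not established.

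Three further points limit the case. Aim 1 targets patients interested in starting PrEP, and Section 9.4 randomizes after consent, so refusal of the ED dose may be rare. Several questionnaires offer a refusal option, so skipping a sensitive item is foreseen and is poor evidence of unwillingness. The statement in Section 16.0 that "Patients who miss one or more than one follow-up assessment will continue in the study" is weak evidence of a contradiction, because missing a call is not refusing one.

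The objection does not supply any statement that day-90 PrEP use is collected for someone who declines or stops the pack.

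**Conclusion.** The point holds as a conflict and a gap. A mandatory withdrawal sentence, read literally, could leave participants without a primary-outcome value, and the sections that treat stopping PrEP as a treatment decision do not say that follow-up continues. Losses could differ between arms and be related to the outcome, and PrEP refusal could be reported as attrition.

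The size is not known. The 2.6 to 12.5 points are an illustration that rests on an assumed number withdrawn, no control withdrawals and all withdrawn iPrEP participants being non-users. Other plausible assumptions give zero or the opposite sign. The differences in the power table are offered there as illustrative rows in an admittedly underpowered pilot, so they should not be read as thresholds against which this bias is judged. The change is worth making because it protects the primary outcome and a stated deliverable at little cost.

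**What to change.** Reword the Section 12.4 sentence along these lines: verbal or nonverbal unwillingness toward a component releases the participant from that component only. The 30-, 60- and 90-day calls and the provider or record verification of PrEP use continue in both arms unless the participant, verbally or nonverbally, declines these as well or withdraws consent. This keeps the nonverbal safeguard, which matters in a trial that enrols adolescents without requiring parental consent.

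Record four separate dated statuses: declined a component, stopped PrEP, declined calls, and withdrew consent to records. Report attrition under Aim 1b from the last two, with refusal and stopping of PrEP shown separately.

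Reconcile Section 12.4 with Sections 9.3, 17.2 and 18.9, including the passages that end participation for a contraindication or a safety concern. Each should say whether day-90 outcome data are still collected after PrEP is stopped. No clinical stopping rule needs to change for this.

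The cost is a few edited sentences, matching consent wording, a status field in REDCap and a few more calls to people not taking PrEP, who remain free to decline. No extra participants or clinical procedures are needed.

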12.5. Vulnerable Subjects, if relevant to your study

Individuals who meet inclusion criteria may be asked to participate in research at times separate from clinical thus institutionalized individuals and prisoners will not be able to participate. Children less than age 13 (or but weighing less than 65lbs.) will be excluded from this research as these individuals are not eligible for

PrEP as it is currently approved by the FDA. It is anticipated that individuals from economically or educationally disadvantaged backgrounds will be enrolled, however special care will be taken to ensure that such individuals understand all aspects of the study and all of their rights as research participants. Urine tests will be conducted to ascertain the pregnancy status of participants and women found to be pregnant will not be able to continue in the study.

13.0. Potential Benefits of the Proposed Research to Research Participants and Others

Participants may directly benefit from the proposed research in several ways. Patients will be educated about PrEP and may discover they are eligible for PrEP based on ED screening. Initiating PrEP, either in the ED or in the out-patient clinic will reduce the likelihood of acquiring HIV. Patients randomized to the experimental arm will have a more rapid initiation of PrEP than those initiation PrEP in the out-patient clinic. If patients randomized to immediate PrEP initiation are adherent to the medication they may achieve earlier protection against HIV infection. If successful, the screening and initiation pathways created during this project could help reduce the HIV acquisition risk of future ED patients and have significant benefits to public health.

14.0. Importance of the Knowledge to be Gained

The proposed research could have a direct impact on future HIV prevention research. Ultimately, the studies proposed may result in improved knowledge on how expand access to PrEP. The proposed RCT will also provide the first data on the impact of ED initiated PrEP. The proposed work will form the foundation for a future multicenter RCT of ED initiated PrEP that could change ED based practice toward incorporating early portions of the PrEP cascade into routine ED based care for high risk individuals.

15.0. INCLUSION OF WOMEN, MINORITIES AND CHILDREN

15.1 Women and Minorities

Women and minorities will be included in the research without exception; no one will be excluded from participation based on sex/gender, race or ethnicity.

15.2. Children

Exclusion of groups: Children will be excluded from this research if they are age less than 13 or age 13-17 but weighing less than 65 lbs. as they are not eligible for PrEP.

16.0 Recruitment and Retention Plan

Participants will be recruited, enrolled and followed during one 12-month study period the MSBI emergency departments during their ED visit. The RA will screen all adult patients using the electronic medical record tracking board; to maximize the likelihood of identifying eligible patients, RAs will prioritize approaching patients with a chief complaint that suggests PrEP eligibility (e.g. penile or vaginal discharge, drug overdose or withdrawal). A HIPAA waiver will be requested for these screening activities.

The RA will obtain permission from the clinical team to approach the patient. At this point, the research coordinator will approach the patient to provide information about the study, and if the potential participant is interested, verbal consent will be sought for PrEP behavioral eligibility screening. Patients that meet behavioral criteria for PrEP and are interested in participating will sign written informed consent will be obtained. Patients will be given a consent form that outlines the purpose of the study, length of time of the study, describe what is involved, their responsibilities if they take part in the research, information regarding compensation, potential its and foreseeable risks where applicable and study contact information. Potential participants will be informed if they would like time to think about the study and review the consent form. If requested, they will be given as much time as needed to review prior to signing the consent form. Participants will be informed of the

data sharing plan and the protections against identification of individuals associated with it. In addition to consenting to the survey, patients will also give consent to allow investigators to collect clinical and sociodemographic data from the medical record via chart review and electronic data capture.

To maximize retention we will use a Locator Form to collect the study participants current address, email address, phone numbers and, with consent, private social media information. In order to facilitate linkage and follow-up, we will also collect similar information for friends and family who know how to reach the patient. All follow-up assessments will be conducted at 30, 60, and 90 from PrEP initiation. All follow-up assessments will be conducted by telephone. Patients will be mailed an appointment reminder and receive a phone call a week and a day before their scheduled assessment. Patients who miss one or more than one follow-up assessment will continue in the study so long as it is within 90 days of their enrollment.

We will provide a \$25 cash incentive for all participants to complete their enrollment, 30, 60 and 90-day follow-up assessments.

